### 5.1.3 3-Week Follow-up

***Note: If the subject does not come to a visit wearing lenses and is not experiencing any problems, it is preferred if the current visit is rescheduled within the visit window.***

***Note: All VA measurements MUST be made using a phoropter.***

**Note:** *The Online Consumer Survey should be completed by the subject before the subject comes into the office for this visit. If it has not been completed prior to coming in, ask subject to complete now.*

- a. Collect changes in ocular medical history and concomitant medications
- b. Collect the following study lens information from the subject:
  - Over the last week, Average number of days per week worn
  - Over the last week, Average daily wearing time, hours per day
  - Over the last week, Average hours of comfortable wear per day
  - Hours lenses worn on the day of this visit
  - Over the last week, average number of times used rewetting drops per day (Note: Only to be completed by subjects reporting rewetting drop use with habitual lenses at the Dispensing Visit.)
- c. Collect the Lens Performance Ratings for study lenses using the 0-100 rating scales provided by the Sponsor.
- d. Collect the Symptoms/Complaints for study lenses.
- e. If the subject did not come to the visit wearing one or more study lenses, go to step f. Otherwise, evaluate the lenses (while on eye) and record the following assessments:
  - Distance (OU), intermediate (OU), and near (OU) lens VA
  - Lens wettability
  - Lens deposits (type, percent, and degree)
  - Lens centration
  - Lens movementCompare the high-contrast OU distance lens VA to the high-contrast OU distance BSCVA obtained at the Screening/Dispensing visit. If the VA has decreased by  $\geq 10$  letters, explain.
- f. Perform a slit lamp examination (remove the lenses if the subject wore lenses to the visit). Record all slit lamp findings and at a minimum sketch the following in the subject's source document:
  - Any ungraded finding marked as "PRESENT"
  - Any corneal scars
  - Any corneal staining
  - Any corneal infiltrate
  - Any other graded slit lamp findings Grade  $>2$
- g. Collect/assess all AEs/ADEs, including serious or significant non-serious AEs. If subject has an ongoing AE at the time of 3-Week Follow up visit, the subject should not be exited. Unscheduled visit (s) should be scheduled to follow upon the AE(s) until the event resolves or stabilizes. Once event resolves or stabilizes, subject may be exited.
- h. Collect all worn and unworn study lenses from the subject.

**Note:** *The Investigator must return all worn and unworn study lenses to the Sponsor in the return materials provided. All study contact lenses must be accompanied by a Product Accountability Log.*

- i. Complete the 3-Week Follow-Up Visit eCRFs. If the subject is discontinued or exited at this visit, complete Exit Visit eCRFs.

#### **5.1.4 Exit Visit**

***Note: All VA measurements MUST be made using a phoropter.***

- a. Indicate status of the subject on the Subject Exit Form. If the status is “Discontinued” or “Non-dispensed,” indicate the PRIMARY exit reason for each eye on the Subject Exit Form.
- b. Collect changes in ocular medical history and concomitant medications
- c. For all subjects, complete an exit ocular examination without lenses on the eyes. Collect the following assessments:
  - Spherocylindrical refraction
  - High-contrast distance (OD, OS, OU) logMAR BSCVA
  - Keratometry

Compare the final visit high-contrast distance (OD, OS) BSCVA to the high-contrast distance (OD, OS) BSCVA obtained at the Screening/Dispensing Visit. If the VA has decreased by  $\geq 10$  letters, explain.

For each eye, compare the final visit keratometry readings to the Screening/Dispensing Visit keratometry readings. If there is a change of 1.00 D or more, explain.

- d. Collect/assess all AEs/ADEs, including serious or significant non-serious AEs.
- e. Collect all worn and unworn study lenses from the subject.

***Note: The Investigator must return all worn and unworn study lenses to the Sponsor in the return materials provided. All study contact lenses must be accompanied by a Product Accountability Log.***

- f. Complete the Investigator survey following the completion of the subject’s final study visit.
- g. Complete the Exit visit eCRFs.

#### **5.1.5 Unscheduled Visits**

Additional visits may be scheduled, as necessary, to ensure the safety and well-being of subjects. All additional exams should be fully documented in the source documents and on Unscheduled Visit eCRFs, as appropriate. Visits intended to fulfill scheduled visit requirements that fall outside the designated scheduled visit range, are not Unscheduled Visits. In these cases, the visit data will be collected and transcribed to the appropriate scheduled visit eCRF.

If a subject is seen for multiple visits during a given visit timeframe, the data from the visit that is intended to meet the protocol requirements for the scheduled visit should be captured on the visit eCRF. Where such a determination cannot be made, the first visit within the scheduled visit interval will be used for completion of the protocol required scheduled visit eCRF. Data from any additional visits within a scheduled visit interval will be captured on an Unscheduled Visit eCRF.

If a subject is only seen for replenishment of study lenses, a complete exam is not required, as long as the subject is not experiencing any problems. If study lenses are replaced, record

the eye, dispensed lens sphere power, add power (high, low, none), and primary replacement reason in the Product Dispensing Only eCRF. Collect worn study lenses from the subject. Record the eye, lens type, add power, sphere power, lot number, and quantity dispensed in the Product Accountability Log.

Subjects who require further follow-up on an AE/SAE upon discontinuation or at the conclusion of the 3-Week Follow-Up Visit will be followed according to the Post-study Follow-up [Section 3.3.4](#). At these follow-up visits, the subject should remove contact lenses s/he may be wearing. Assessments will be performed according to the investigator's judgement. The Investigator is required to follow the subject until the condition no longer warrants further follow-up for study purposes.

***Note: All VA measurements MUST be made using a phoropter.***

- a) Indicate the reason for the Unscheduled Visit.

***Note: If the subject is experiencing problems, complete the entire Unscheduled Visit Form.***

- b) Collect the following information from the subject regarding study lenses:
  - Average number of days per week worn
  - Average daily wearing time, hours per day
  - Average hours of comfortable wear per day
  - Hours lenses worn on the day of this visit
  - Rewetting drop use.
- c) Collect Symptoms/Complaints.
- d) If the subject did not come to the visit wearing one or more study lenses, go to step e. Otherwise, evaluate the study lenses (while on eye), and record the following assessments:
  - Distance (OU), intermediate (OU), and near (OU) lens VA
  - Lens wettability
  - Lens deposits
  - Lens centration
  - Lens movementCompare the high contrast OU distance lens VA to the high contrast OU distance BSCVA obtained at the Screening/Dispensing Visit. If the VA has decreased by  $\geq 10$  letters or more, explain.
- e) Perform a slit lamp examination (remove the lenses if the subject wore lenses to the visit). Record all slit lamp findings and at a minimum sketch the following in the subject's source document:
  - Any ungraded finding marked as "PRESENT"
  - Any corneal scars
  - Any corneal staining
  - Any corneal infiltrate
  - Any other graded slit lamp findings Grade  $>2$
- f) If an unscheduled lens replenishment for the same lens is required, dispense additional lenses, and collect the following:
  - Primary reason for replacement

- Dispensed lens sphere power
- Dispensed lens add power (high, low)
- Distance (OU), intermediate (OU), and near (OU) lens VA
- Lens wettability
- Lens centration
- Lens movement

**Note:** *Remember to record replenishment on the Product Accountability Log.*

**Note:** *The Investigator must return all worn and unworn study lenses to the Sponsor in the return materials provided. All study contact lenses must be accompanied by a Product Accountability Log.*

- If an unscheduled lens replacement requires a change in lens power for unacceptable vision, follow steps f, g, h, and i in [Section 5.1.2](#).
- The Unscheduled Visit eCRFs should be completed.

If the subject is discontinued or exited at this visit, complete the Exit Visit eCRFs.

#### **5.1.6 Missed Visits**

If a subject misses any scheduled follow-up visit, the visit is considered missed. Indicate a missed visit on the eCRF for that scheduled visit. Schedule the subject for an Exit Visit as soon as possible. If the subject cannot be reached or rescheduled, the subject should be recorded as Lost to Follow-Up.

#### **5.1.7 Product Dispensing Only Visit**

If a subject is seen for resupply or replacement of study materials and the subject is not experiencing any problems, a complete exam is not required. If any assessment is performed, then an Unscheduled Visit Form must be completed instead of a Product Dispensing Only Form.

If study lenses are dispensed, collect the following information in the source document for each being dispensed, and transcribe to the Product Dispensing Only eCRF Form:

- Visit date
- Subject ID number
- Primary reason for lens replacement
- Dispensed lens power, add power

Record the sphere power/add, lot number, quantity dispensed, and for which eye the lenses are being dispensed in the Product Accountability Log.

**Note:** *The Investigator must return all worn and unworn study lenses to the Sponsor in the return materials provided. All study contact lenses must be accompanied by a Product Accountability Log.*

#### **5.1.8 Post Study Follow-up**

If a subject requires discontinuation or is completing the study, but has an ongoing AE, the subject should not be exited until the event resolves or stabilizes. This may imply that follow-up will continue via Unscheduled visits, and that additional evaluations may be requested by the Sponsor.

Investigator must schedule Unscheduled Visits, as necessary.

**Note:** *All VA measurements MUST be made using a phoropter.*

- a) Remove any contact lenses the subject may be wearing. Perform a slit lamp examination. Record and sketch the ocular results and findings in the subject's source document
- b) Complete an ocular examination without lenses on the eyes, including spherocylindrical refraction and distance (OD, OS, OU) BSCVA
- c) The Investigator is required to follow the subject until the condition no longer warrants further follow-up for study purposes. An Unscheduled Visit eCRF must be completed for each of these visits

Once AE has resolved or stabilized, the Investigator may proceed with completing the exit visit

## 5.2 Questionnaires and Surveys

### 5.2.1 Baseline Questionnaire

Each eligible subject will complete a questionnaire prior to study lens insertion. Responses will be regarding current habitual lens wear.

### 5.2.2 Online Consumer Survey

Each subject will be required to complete a Subjective Assessment through an internet survey. Each enrolled subject will be provided with an internet address to access **at least 7 days after the 1-Week Follow-Up Visit but before the 3-Week Follow-Up Visit**. Each subject will be provided with a confidential unique ID and password (login) in order to access the online survey. If the user forgets their password, there will be a "forgot password" option within the system. The system will send reminders to the subject via email or mobile alerts. The study coordinator will call the subject prior to the visit date to remind the subject to complete the survey.

There will be a specified timeframe in which the survey must be completed. The Investigator will provide the market research firm with the subject's email address. If the subject has not completed the survey during the specified duration, the market research firm may contact that subject by email with a reminder to complete the survey. If the subject has not completed the survey by the time of the 3-Week Follow-Up Visit, the subject may complete it at that time.

### 5.2.3 Investigator Survey

The Investigator (or designee) will complete a survey to answer questions about each subject's study lens wear at the subject's Exit Visit. This information will be collected within the eCRF system.

## 5.3 Study Completion / Early Study Terminations / Suspensions

### 5.3.1 Study Completion

For purposes of the Investigator notifying the IRB, the study is complete when all subjects at the sites have been exited. Sponsor approval is required prior to IRB notification.

### **5.3.2 Early Study Termination/Suspension**

If during the study it becomes evident to the Sponsor that the study should be stopped prematurely or placed on hold, appropriate notification will be given to the Investigator(s) IRBs, and United States Food and Drug Administration (FDA), as applicable. Bausch + Lomb will instruct the Investigators to stop/restart dispensing study materials and will arrange for study closeout, if applicable, at each site.

### **5.4 Concomitant Medications/Therapy**

Other contact lenses are not allowed to be used by subjects during the study.

Ocular medications or systemic or topical medications that, in the Investigator's opinion, could potentially affect ocular physiology or lens performance are prohibited during the course of the study.

### **5.5 Treatment Compliance**

Treatment compliance will be assessed using lens wear parameter data.

### **5.6 Protocol Deviations**

A deviation from the protocol is an unintended and/or unanticipated departure from the procedures and/or processes approved by the Sponsor and the IRB and agreed to by the Investigator. It is a Sponsor expectation that Investigators will follow the protocol and procedures as written. The Sponsor will not grant protocol waivers for this study. The Investigator may implement a deviation from the protocol to eliminate an immediate hazard to study subjects without prior IRB approval. As soon as possible after such an occurrence, the implemented deviation, as well as the reasons for it should be submitted to the IRB for review and approval. It should also be submitted to the Sponsor for agreement, and to the regulatory authorities, if required.

In the event a protocol deviation occurs, the date of and reason for deviations must be documented in all cases. Significant or major protocol deviations impacting the rights or safety of the subject, or the integrity of the study must be reported by the Investigator to the IRB and Medical Monitor immediately. Reporting of all other protocol deviations must adhere to the requirements of the governing IRB. Unless the protocol deviations put the subject at risk or the subject's condition requires that they be discontinued from the study, subjects may continue to participate until the end of the study.

Site Corrective Action Plans will be developed and completed as deemed necessary by the Sponsor, Sponsor designee (e.g., CRO) for sites or Investigators who deviate from this protocol in a way that adversely affects the rights, safety, or well-being of the subject(s) and/or the quality or integrity of data. The Site Corrective Action Plan will outline the deviation and the site's corrective and/or remedial actions. Decisions regarding critical deviations that merit Investigator disqualification and site closure will be made by the Sponsor and documented in the Trial Master File.

## **6.0 ADVERSE EVENTS**

### **6.1 Introduction to Adverse Event Definitions**

Adverse events, serious AEs (SAEs), significant non-serious AEs, non-significant non-serious AEs, adverse device effects (ADEs), anticipated serious adverse device effects

(ASADEs), and unanticipated adverse device effects (UADEs) are defined in this section and in the protocol's glossary.

An AE is any untoward medical occurrence, unintended disease or injury, or untoward clinical signs (including abnormal laboratory findings) in subjects, users, or other persons, whether or not related to the investigational medical device, comparator, or the procedures involved. For users or other persons, this definition is restricted to events not related to investigational medical devices.

### 6.1.1 Serious Adverse Event (SAE) Definitions

An AE that (related or not related to the investigational test articles, comparator products or study procedures):

- Led to death.
- Led to serious deterioration in the health of the subject, that resulted in:
  - A life-threatening illness or injury; or
  - A permanent impairment of a body structure or a body function (e.g., blindness); or
  - Inpatient or prolonged hospitalization; or
  - Medical or surgical intervention to prevent life-threatening illness or injury or permanent impairment to a body structure or a body function.
- Led to fetal distress, fetal death, or a congenital abnormality or birth defect.

*Note: A planned hospitalization for a pre-existing condition, or a procedure required by the protocol, without serious deterioration in health, is not considered an SAE.*

Serious adverse events may include but are not limited to any hazardous, sight-threatening conditions occurring after exposure to the investigational test article or control product including, but not limited to, the following:

- A presumed infectious ulcer (defined as a progressive erosion of the corneal tissue). For the purposes of reporting, this includes:
  - Central or para-central location
  - Penetration of Bowman's membrane
  - Infiltrate  $\geq 2$  mm diameter
  - Associated with iritis
  - Associated with any increase in intraocular pressure
  - Culture positive for microorganisms
  - Increasing size or severity at subsequent visits

*NOTE: Signs of a presumed infectious corneal ulcer may include irregular focal infiltrates, active lesions with raised edges, significant diffuse infiltration, anterior corneal to mid-stromal involvement, erosion with overlying staining, conjunctival and lid edema, anterior chamber reaction (iritis), and severe bulbar and limbal redness. Symptoms associated with a presumed infectious ulcer (microbial keratitis) may include pain of rapid onset, severe redness, purulent or mucopurulent discharge, tearing, and photophobia.*

- Any central or paracentral (within 6 mm of cornea) corneal event that results in permanent opacification (such as corneal scar or vascularization)
- Any serious adverse ophthalmic events including hypopyon and/or hyphema
- Any neovascularization within the central 6 mm of the cornea
- Permanent loss of  $\geq 2$  lines of BSCVA
- All cases of iritis.

### **6.1.2 Significant Non-Serious Adverse Event Definitions**

A significant non-serious adverse event is an AE that does not meet the serious criteria, is considered significant by the Sponsor, and requires expedited reporting to the Sponsor (see [Section 6.2.1](#)). These events include but are not limited to:

- Peripheral non-progressive non-infectious corneal ulcers
- All symptomatic corneal infiltrative events
- All cases of corneal staining greater than or equal to Grade 3
- A temporary loss of two or more lines of BSCVA (for greater than or equal to 2 weeks)
- Neovascularization cases Grade 2 or greater (if not within 6 mm of the cornea)
- Any ocular event that necessitates temporary lens discontinuation of greater than or equal to 2 weeks.

### **6.1.3 Non-Significant Non-Serious Adverse Events Definitions**

A non-significant non-serious adverse event may include but are not limited to the following and does not require expedited reporting:

- Bacterial Conjunctivitis;
- Viral Conjunctivitis;
- Allergic Conjunctivitis;
- Corneal Edema;
- Contact Lens Related Papillary Conjunctivitis; and,
- Loss of Contrast Sensitivity

### **6.1.4 Adverse Device Effect (ADE) Definitions**

An adverse device effect is an AE that is assessed to be related to the use of an investigational medical device. This definition includes AEs resulting from insufficient or inadequate instructions for use; deployment, implantation, installation, or operation; or any malfunction of the investigational medical device. This definition also includes any event resulting from use error or from intentional misuse of the investigational medical device.

#### **6.1.4.1 Anticipated Serious Adverse Device Effect (ASADE) Definition**

An anticipated serious adverse device effect (ASADE) is an ADE that first meets the serious criteria (see [Section 6.1.1](#)) and which, by its nature, incidence, severity or outcome, has been previously identified in the investigational plan or application (including a

supplementary plan or application) and/or in the risk analysis report. ASADEs include but are not limited to:

- Corneal Ulcer (infectious or non-infectious)
- Keratitis
- Sensitivity to light (photophobia)
- Excessive eye secretions including mucopurulent discharge
- Blurred vision, rainbows, or halos around objects
- Poor visual acuity (reduced sharpness of vision)
- Moderate to severe eye pain not relieved by removing the lens

#### **6.1.4.2 Unanticipated Serious Adverse Device Effect (USADE) Definitions**

An unanticipated serious ocular or non-ocular adverse device effect is an adverse event related to the use of an investigational medical device that has resulted in any of the consequences characteristic of a serious adverse event as described in [Section 6.1.1](#) and which by its nature, incidence, severity or outcome has not been identified in the current version of the risk analysis report.

This definition includes but is not limited to AEs resulting from insufficient or inadequate instructions for use, deployment, implantation, installation, or operation, or any malfunction of the investigational medical device.

This definition also includes any event resulting from use error or from intentional misuse of the investigational medical device. USADEs include but are not limited to

- Any central or paracentral (within 6 mm of cornea) corneal event that results in permanent opacification (such as corneal scar or vascularization)
- Any serious adverse ophthalmic events including hypopyon and/or hyphema
- Any neovascularization within the central 6 mm of the cornea
- Permanent loss of  $\geq 2$  lines of BSCVA
- All cases of iritis.

#### **6.1.5 Relationship Definition: Study Device and/or Other Study Materials**

- **Related:** There is at least a reasonable possibility that the AE is related to the study device (study solution) and/or rewetting drops. Reasonable possibility means that there is evidence to suggest a causal relationship or association between the study device and/or rewetting drops and the AE.
- **Not related:** There is little or no reasonable possibility that the AE is related to the study device (study solution) and/or rewetting drops. This assessment implies that the AE has no evidence to suggest either a causal relationship or association to the study device and/or Rewetting Drops and a more likely or certain alternative etiology exists.

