#### **3.3.1.2 Exclusion Criteria**

1. Subjects participating in any drug or device clinical investigation within 30 days prior to entry into this study and/or plan to do so during the period of study participation
2. Subjects who are women of childbearing potential (those who are not surgically sterilized or postmenopausal) are excluded from participation in the investigation if they meet any one of the following conditions:
  - She is currently pregnant

- She plans to become pregnant during the study
- She is breastfeeding

3. Subjects with any systemic disease currently affecting ocular health or that, in the Investigator's opinion, may have an effect on ocular health during the course of the study
4. Subjects with an active ocular disease
5. Subjects who have had any corneal surgery (e.g., refractive surgery)
6. Subjects who have worn gas-permeable (GP) contact lenses within the last 30 days or who have worn polymethylmethacrylate (PMMA) lenses within the last 3 months
7. Subjects who currently wear monovision or toric contact lenses
8. Subjects who are not correctable to 32 letters (0.3 logMAR) with bilateral soft multifocal contact lenses
9. Subjects with an ocular astigmatism >1.00 D in either eye
10. Subjects with anisometropia (spherical equivalent) >2.00 D
11. Subjects with any Grade  $\geq 2$  finding during the slit lamp examination. Subjects with corneal infiltrates of ANY GRADE are not eligible
12. Any "Present" finding during the slit lamp examination that, in the Investigator's opinion, interferes with contact lens wear
13. Any scar or neovascularization within the central 6 mm of the cornea. Subjects with minor peripheral corneal scarring (that does not extend into the central area) that, in the Investigator's opinion, does not interfere with contact lens wear are eligible for this study
14. Subjects who are amblyopic
15. Subjects using any systemic or topical ocular medication that will, in the Investigator's opinion, affect ocular physiology or lens performance
16. Subjects who are allergic to any component in the study care products

If a subject meets all the inclusion criteria and does not exhibit any of the exclusion criteria, the subject is eligible for entry into the study. Ineligible subjects MUST NOT be enrolled in this study. Any subject enrolled in the study who later is found to have not met the eligibility criteria at entry will be discontinued.

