#### 4.5 Other Materials

All subjects will be dispensed lens cases for return of dry-stacked worn study lenses to the Investigator during the study. Subjects that habitually use rewetting drops may continue to use their drops. ***OTHER CONTACT LENS CARE PRODUCTS ARE NOT ALLOWED TO BE USED.***

Investigators will return all worn and unworn study lenses to the Sponsor at the end of the study.

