## **6.2.3 Device Deficiencies: Definition and Reporting Procedures**

A device deficiency is defined as an inadequacy of a medical device with respect to its identity, quality, durability, reliability, safety, or performance. Device deficiencies include malfunctions, use errors, and inadequate labeling.

Investigators must evaluate, record, and report any complaints/ deficiencies or malfunctions experienced with the study solution during this trial to the Medical Monitor

promptly. The Sponsor and Medical Monitor shall review all device deficiencies, and, upon the Sponsor's request, Investigators must supply any additional information related to the safety reporting of a particular event.

Report device deficiencies within 24 hours of knowledge to:

The Medical Monitor will distribute, within 24 hours of knowledge, all device deficiencies to the Sponsor.

The Sponsor shall review all device deficiencies and determine and document in writing whether they could have led to an SAE. In the event of a disagreement between the Sponsor and the Investigator(s), the Sponsor shall communicate both opinions to the reviewing IRB per their established reporting procedures and the health authority.

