6.5.12 Safety Analyses

6.5.12.1 Adverse Events

All adverse events occurring during the study will be recorded and classified to below categories on the basis of MedDRA terminology, the number and percentage of each category will be summarized.

- AEs (NOT Device Related)
- Serious Adverse Events (SAEs) (NOT Device Related)
- Adverse Device Effects (ADE) (Device Related)
- Unanticipated Serious Adverse Device Effects (USADE) (Device Related)
- Anticipated Serious Adverse Device Effects (ASADE) (Device Related)

A treatment-emergent AE (TEAE) is defined as any AE with an onset on or after the date of the first study device use. If the start date of an AE is incomplete or missing, then the AE will be considered as a TEAE unless a partial date shows it as a pre-treatment event. All reported treatment-emergent AEs (TEAEs) will be summarized by the number of subjects reporting AEs, system organ class, preferred term, severity, seriousness, and relationship to study device.

Ocular Adverse events will be summarized as well by the number of subjects/eyes reporting AEs, system organ class, preferred term, severity, and relationship to study device. Ocular adverse events are defined as AEs specified in one or both eyes. Only treatment-emergent adverse events (TEAEs) are included in the summary.

If more than one AE is coded to the same preferred term for a subject, the subject will be counted only once for that preferred term using the most severe and most related occurrence for the severity and relationship to study intervention summaries, respectively.

If the severity of a TEAE is missing, the maximum severity will be assigned to the event for the summaries by severity. The value will be displayed as missing in the data listings.

If the relationship to the study intervention is missing for a TEAE, the event will be considered related to the study intervention for the summaries. The value will be displayed as missing in the data listings.

All information pertaining to AEs noted during the study will be listed by subject, detailing verbatim given by the investigator, preferred term, system organ class, start date, stop date, severity, actions taken, and device relatedness. The AE onset will also be shown relative (in

Page 31 of 44 – CONFIDENTIAL

number of days) to the day of initial use of the study device. In addition, a list of subjects who experienced SAEs will also be provided.

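### Protocol 6.1.5 names a study solution and accepts rewetting drops as a cause of a Related event, so drop-only events can be tabulated as device-related in a lens trial

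*Protocol*

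**What the plan says.** Protocol 4.1 describes one investigational article, the kalifilcon A daily disposable multifocal lens. The only solution named with it is the saline in the blister pack. Besides lenses, subjects receive cases for their worn lenses (Protocol 4.5 and Appendix C). Other care products are forbidden, with one exception: "Subjects that habitually use rewetting drops may continue to use their drops".

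Three places in the protocol describe a different set of products:

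- **Relatedness, 6.1.5.** The definition of Related is: "There is at least a reasonable possibility that the AE is related to the study device (study solution) and/or rewetting drops". The definition of Not related carries the same parenthesis. The sentence explaining Related drops it and speaks of an "association between the study device and/or rewetting drops and the AE".
- **Device deficiencies, 6.2.3.** The section opens generically: "A device deficiency is defined as an inadequacy of a medical device with respect to its identity, quality, durability, reliability, safety, or performance". The sentence that imposes the duty is narrower: "Investigators must evaluate, record, and report any complaints/ deficiencies or malfunctions experienced with the study solution during this trial".
- **Exclusion 16, 3.3.1.2** (also in the synopsis and SAP 6.2): "Subjects who are allergic to any component in the study care products".

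SAP 6.5.12.1 classifies events as not device-related or as one of three device-related kinds, the first being "Adverse Device Effects (ADE) (Device Related". It also plans summaries by relationship to the study device.

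**The concern.** The wording in 6.1.5 is operative. Protocol 6.2 lists what the investigator must decide about each event, and item d, relationship to the study device, refers to 6.1.5. Two faults follow.

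First, rewetting drops are an alternative cause within the definition of Related, although they are neither the device nor supplied by the sponsor. One answer then covers two products. Drop use is asked about at baseline and at both follow-up visits (Protocol 5.1.1 to 5.1.3), so attribution to drops is foreseeable.

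Second, the parenthesis equates the device with a solution. A literal reader could weigh causality against something the subject never received.

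At stake are the ADE categories and the by-relationship tables (14.3.1.5.1 and 14.3.1.5.2 in SAP 7.1). A serious event may also be affected, because classification as an unanticipated serious device effect starts a reporting clock to the IRB (Protocol 6.2.1). If relatedness is captured as one combined entry, it cannot be reliably split into lens and drops afterwards.

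**Working it through.** The check is a comparison of texts. The plan's one computed design figure, 93% power with 270 subjects, does reproduce: the exact one-sided test needs 150 of 270 agreeing (exact alpha 0.0387) and has power 0.939 at a true proportion of 0.6. It is not an input here, and no correction to the safety wording changes it.

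**Step 1: is a study solution or care product supplied?** Protocol 4.0, 4.1, 4.3, 4.5 and Appendix C describe lenses and lens cases, and the subject's own drops. The packaging saline is never called the study solution. The one contrary hint is the synopsis, which allows for eye drops that are provided; no other section describes any, and 4.3 and 4.5 speak only of habitual drops.

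**Step 2: follow one event.** Take an adverse event that the investigator attributes to the subject's own drops and to nothing else.

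| Text | Result for this event |
|---|---|
| Protocol 6.1.5 | Related, since drops alone suffice |
| Protocol 6.1.4 | Not an ADE, since that requires a relation to use of the investigational device |
| Protocol 6.2, item d | The question concerns the device, but the answer is taken from 6.1.5 |
| SAP 6.5.12.1 | Device-related or not; no place for drops |

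The protocol gives two answers, and the SAP has no rule for choosing between them. If the entry from 6.1.5 feeds the SAP tables directly, the event counts as device-related.

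**Step 3: deficiencies.** In 6.2.3 only the sentence on evaluating, recording and reporting names the study solution. The definition before it and the 24-hour rule after it cover any device deficiency, and the Glossary entry refers to the investigational device. The section is inconsistent, but lens deficiencies remain within its definition and its 24-hour rule. SAP 7.1 and 7.2 plan no deficiency table or listing, so an omission would not show in the planned output. Unscheduled lens replacements are tabulated by reason (SAP 6.5.10.5.3), which gives partial cover.

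**Step 4: exclusion 16.** It names no supplied care product and does not mention the lens material or packaging solution. It bears on eligibility, not on event counts or deficiency reports.

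**The case against.** The strongest reply is that this is leftover wording with little practical effect. The term defined in 6.1.5 is still the study device, and its explanatory sentences omit the gloss. ADEs and their unanticipated serious form are tied to the investigational device in 6.1.4 and 6.1.4.2. SAP 6.5.12.1 says study device throughout its category labels, and no investigator is likely to mistake a lens for a solution. The heading of 6.1.5 mentions other study materials, so including drops may be deliberate. Appendix C also tells subjects to use a rewetting solution on a sticking lens, so some drop use belongs to the lens instructions, and 6.1.4 counts harm from inadequate instructions as an ADE. Any error would be over-inclusion in descriptive safety tables.

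Much of this stands. A reader might infer that the device-related counts as a whole rest on the wrong product, or that torn or mislabelled lenses fall outside the deficiency rule. The documents do not support either reading, because the surrounding definitions point to the device and the definition and 24-hour rule in 6.2.3 are generic.

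The conflict over drop-only events remains. A deliberate choice to include drops would still need its own entry, because 6.1.4 does not make every drop-related event an ADE. The case of the sticking lens is a reason to say that drop attribution does not by itself make an ADE; it is not a reason to merge the two causes.

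**Conclusion.** The point holds as a conflict between definitions with a possible effect on safety classification. Events attributed only to the subject's own drops are Related under 6.1.5, are not ADEs under 6.1.4, and can be counted as device-related under the SAP. The study-solution wording in 6.1.5 and 6.2.3 is an ambiguity.

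This rests on two assumptions: that the eCRF, which is not among the documents, has a single relationship field, and that the SAP tables are built from it.

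The size cannot be calculated. A reader might try to put a figure on it: if 2% to 5% of 300 subjects had a related event (6 to 15) and two of those were drop-only, the drop-only share would be 2/15 = 13% to 2/6 = 33%. Neither the rate nor the two events comes from the documents, so this is not evidence of bias of that size. Two subjects would be 2/300 = 0.7% of those enrolled.

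The primary analysis uses a survey response and is unaffected.

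**What to change.** 1. In Protocol 6.1.5, replace the reference to a study solution, in both definitions, with the study lens including its packaging solution.
2. Record relationship to rewetting drops as a separate item that does not by itself make an event an ADE. State in SAP 6.5.12.1 that the device-related categories and by-relationship tables use the lens item.
3. In Protocol 6.2.3, replace study solution with study lens so that the reporting sentence matches the definition and the 24-hour rule around it.
4. Reconcile exclusion 16 (Protocol synopsis and 3.3.1.2, SAP 6.2) and the synopsis reference to provided eye drops with the products described in Protocol 4.1, 4.3 and 4.5.

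The cost is protocol wording, a matching line in the SAP and one eCRF field. No visit or procedure is added. The change should be made before adverse events are entered.
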